10.8. Analysis of safety

Analysis of safety relative to the primary epoch will include analysis of safety data collected following administration of the three primary doses of study vaccine. Analysis of safety relative to the booster epoch will include analysis of safety data collected following administration of the booster dose of study vaccine. At this second stage, in

order to avoid missing SAEs that have been reported, an SAE summary table including all the events reported during the entire study period will also be generated.

The analysis will be based on the Total vaccinated cohort for both primary and booster epochs. All analyses are descriptive.

- The overall percentage of subjects/doses with at least one local symptom (solicited or unsolicited), with at least one general symptom (solicited or unsolicited) and with any symptom (solicited or unsolicited) during the 4-day (Days 0-3) solicited follow-up period will be tabulated with exact 95% CI [Clopper, 1934] after each vaccine dose and overall primary doses. The same calculations will be done for symptoms (solicited or unsolicited) rated as grade 3 in intensity, for symptoms (solicited or unsolicited) leading to medical advice and for symptoms (solicited or unsolicited) assessed as causally related to vaccination.
- The overall percentage of subjects/doses and of subjects reporting each individual solicited local and general symptom during the 4-day (Days 0-3) solicited follow-up period will be tabulated after each vaccine dose and overall primary doses, with exact 95% CI [Clopper, 1934] after each vaccine dose and overall primary doses. The same calculations will be done for each individual solicited symptom rated as grade 3 in intensity and for each individual solicited symptom assessed as causally related to vaccination.
- Occurrence of fever will be reported per 0.5°C cumulative increments.

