6.4. Analysis of safety**6.4.1. Analysis of safety planned in the protocol**

Analysis of safety relative to the primary epoch will include analysis of safety data collected following administration of the three primary doses of study vaccine. Analysis of safety relative to the booster epoch will include analysis of safety data collected following administration of the booster dose of study vaccine. At this second stage, in order to avoid missing SAEs that have been reported, an SAE summary table including all the events reported during the entire study period will also be generated.

The analysis will be based on the Total vaccinated cohort for both primary and booster epochs. All analyses are descriptive.

- The overall percentage of subjects/doses with at least one local symptom (solicited or unsolicited), with at least one general symptom (solicited or unsolicited) and with any symptom (solicited or unsolicited) during the 4-day (Days 0-3) solicited follow-up period will be tabulated with exact 95% CI after each vaccine dose and overall primary doses. The same calculations will be done for symptoms (solicited or unsolicited) rated as grade 3 in intensity, for symptoms (solicited or unsolicited) leading to medical advice and for symptoms (solicited or unsolicited) assessed as causally related to vaccination.
- The overall percentage of subjects/doses and of subjects reporting each individual solicited local and general symptom during the 4-day (Days 0-3) solicited follow-up period will be tabulated after each vaccine dose and overall primary doses, with exact 95% CI after each vaccine dose and overall primary doses. The same calculations will be done for each individual solicited symptom rated as grade 3 in intensity and for each individual solicited symptom assessed as causally related to vaccination.
- Occurrence of fever will be reported per 0.5°C cumulative increments.

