11. ANNEX 1 STANDARD DATA DERIVATION RULE AND STATISTICAL METHODS

11.1. Statistical Method References

The exact two-sided 95% CIs for a proportion within a group will be the Clopper-Pearson exact CI [Clopper CJ, Pearson ES. The use of confidence or fiducial limits illustrated in the case of binomial. *Biometrika*. 1934;26:404-413].

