11.2.2. Dose number

- The study dose number is defined in reference to the number of study visits at which vaccination occurred. More specifically dose 1 refers to all vaccines administered at the first vaccination visit while dose 2 corresponds to all vaccinations administered at the second vaccination visit even if this is the first time a product is administered to the subject.
- Relative dose: the relative dose for an event (AE, medication, vaccination) is the most recent study dose given before an event. In case the event takes place on the day a study dose is given, the related dose will be that of the study dose, even if the event actually took place before vaccination. For instance, if an adverse event begins on the day of the study vaccination but prior to administration of the vaccine, it will be assigned to this dose. In case a study dose is not administered and an event occurs after the subsequent study dose (eg 3rd study dose), the relative dose of the event will be study dose associated to the subsequent study dose (eg dose 3).
- The number of doses for a product is the number of time the product was administered to a subject.
- The incidence per dose is the number of vaccination visits at which an event was reported among all vaccination visits.

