	3	Severe: Not eating at all

*Fever is defined as temperature $\geq 37.5^{\circ}\text{C} / 99.5^{\circ}\text{F}$ for oral, axillary or tympanic route, or $\geq 38.0^{\circ}\text{C} / 100.4^{\circ}\text{F}$ for rectal route.

The maximum intensity of local injection site redness/swelling will be scored at GSK Biologicals as follows:

0	:	Absent
1	:	≤ 5 mm
2	:	> 5 mm and ≤ 20 mm
3	:	> 20 mm

CONFIDENTIAL

116194 [DTPA-IPV (INFANRIX-IPV)-061]

Statistical Analysis Plan Amendment 2 Final

The maximum intensity of fever will be scored at GSK Biologicals as follows:

Axillary/Tympanic/Oral

0	:	< 37.5°C / 99.5°F
1	:	≥ 37.5°C / 99.5°F and ≤ 38.0°C / 100.4°F
2	:	> 38.0°C / 100.4°F and ≤ 39.0°C / 102.2°F
3	:	> 39.0°C / 102.2°F

In case temperature is recorded rectally, a conversion to Axillary temperature will be performed by removing 0.5°C.

Note that for all tables described in this section, the way the percentage of subjects will be derived will depend on the event analysed (see table below for details). As a result, the N value will differ from one table to another.

Event	N used for deriving % per subject for Vaccination phase	N used for deriving % per dose for Vaccination phase
Concomitant vaccination	All subjects with study vaccine administered	All study visits with study vaccine administered
Solicited general symptom	All subjects with solicited symptoms documented as present or absent for at least one dose.	All doses with solicited symptoms documented as present or absent within 0-3 days post dose
Unsolicited symptom	All subjects with study vaccine administered	All study visits with study vaccine administered
Concomitant medication	All subjects with study vaccine administered	All study visits with study vaccine administered

For summaries by MedDRA primary preferred term combining solicited and unsolicited adverse events, solicited adverse events will be coded as per the following MedDRA codes

Solicited symptom	Lower level term code	Corresponding Lower level term decode
Drowsiness	10013649	Drowsiness
Fever	10016558	Fever
Irritability/Fussiness	10022998	Irritability
Loss of appetite	10003028	Appetite lost
Pain	10022086	Injection site pain
Redness	10022098	Redness at injection site
Swelling	10053425	Swelling at injection site

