13. ANNEX 3: STUDY SPECIFIC MOCK TFL

The following draft study specific mock TFLs will be used.

The data display, title and footnote are for illustration purpose and will be adapted to the study specificity as indicated in the TFL TOC.

These templates were copied from recent studies. Note that there may be few changes between the study specific SAP mock TFL and the final TFLs. These editorial/minor changes will not lead to a SAP amendment.

CONFIDENTIAL

116194 [DTPA-IPV (INFANRIX-IPV)-061]
 Statistical Analysis Plan Amendment 2 Final

Template 1 Number of subjects enrolled by center – TVC

Center	Combo group		Control group		Total	
	n	n	n	n	%	
PPD	20	21		41	9.1	
PPD	27	28		55	12.2	
PPD	7	7		14	3.1	
PPD	16	16		32	7.1	
PPD	27	26		53	11.8	
PPD	26	26		52	11.5	
PPD	25	25		50	11.1	
PPD	23	24		47	10.4	
PPD	22	22		44	9.8	
PPD	24	25		49	10.9	
PPD	7	7		14	3.1	
All	224	227		451	100	

<group description>

n = number of subjects included in each group or in total for a given center or for all centers

All = sum of all subjects in each group or in total (sum of all groups)

% = n/All x 100

Template 2 Number of subjects vaccinated, completed and withdrawn with reason for withdrawal at Visit 3 - TVC

	HRV Liq	HRV LYO	Total
Number of subjects vaccinated	300	300	1200
Number of subjects completed	298	297	1193
Number of subjects withdrawn	2	3	7
Reasons for withdrawal :			
Serious Adverse Event	0	1	1
Non-serious adverse event	0	0	0
Protocol violation	0	0	0
Consent withdrawal (not due to an adverse event)	1	2	4
Migrated/moved from study area	1	0	2
Lost to follow-up (subjects with incomplete vaccination course)	0	0	0
Lost to follow-up (subjects with complete vaccination course)	0	0	0
Others	0	0	0

HRV LIQ = HRV vaccine liquid formulation

HRV LYO = HRV vaccine HRV Lyophilised formulation

Vaccinated = number of subjects who were vaccinated in the study

Completed = number of subjects who completed study visit 3

Withdrawn = number of subjects who did not come for study visit 3

CONFIDENTIAL
 116194 [DTPA-IPV (INFANRIX-IPV)-061]
 Statistical Analysis Plan Amendment 2 Final

Template 3 Number of subjects at each visit and list of withdrawn subjects (TVC)

Group	VISIT	N	Withdrawn Subject numbers	Reason for withdrawal
HRV Liq	VISIT 1	508		
			no. PP	CONSENT WITHDRAWAL
			no. PP	CONSENT WITHDRAWAL
			no. PPD	CONSENT WITHDRAWAL
	VISIT 2	504	no. PPD	CONSENT WITHDRAWAL
			no. PPD	CONSENT WITHDRAWAL
			no. PPD	CONSENT WITHDRAWAL
				SERIOUS ADVERSE EXPERIENCE
	VISIT 3	501		

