		Any symptom			General symptoms			Local symptoms								
		95% CI		95% CI		95% CI		95% CI		95% CI		95% CI		95% CI		
	Group	N	n	%	LL	UL	N	n	%	LL	UL	N	n	%	LL	UL
Dose 2	Combo group	224	18	8.0	4.8	12.4	224	7	3.1	1.3	6.3	224	12	5.4	2.8	9.2
	Control group	227	15	6.6	3.7	10.7	227	6	2.6	1.0	5.7	227	11	4.8	2.4	8.5
Dose 4	Combo group	224	29	12.9	8.8	18.1	224	6	2.7	1.0	5.7	224	26	11.6	7.7	16.5
	Control group	227	29	12.8	8.7	17.8	227	9	4.0	1.8	7.4	227	22	9.7	6.2	14.3
Dose 6	Combo group	224	25	11.2	7.4	16.0	224	8	3.6	1.6	6.9	224	18	8.0	4.8	12.4
	Control group	227	19	8.4	5.1	12.8	227	2	0.9	0.1	3.1	227	18	7.9	4.8	12.2
Overall/dose	Combo group	672	72	10.7	8.5	13.3	672	21	3.1	1.9	4.7	672	56	8.3	6.4	10.7
	Control group	681	63	9.3	7.2	11.7	681	17	2.5	1.5	4.0	681	51	7.5	5.6	9.7
Overall/subject	Combo group	224	60	26.8	21.1	33.1	224	21	9.4	5.9	14.0	224	44	19.6	14.7	25.5
	Control group	227	47	20.7	15.6	26.6	227	14	6.2	3.4	10.1	227	39	17.2	12.5	22.7

Combo group = Subjects received DTPa-IPV/Hib vaccine as a single injection at 2, 4 and 6 months of age

Control group = Subjects received DTPa-IPV and Hib vaccines at different injection sites at 2, 4 and 6 months of age

For each dose and overall/subject:

N = number of subjects with at least one administered dose

n/% = number/percentage of subjects presenting at least one type of symptom whatever the study vaccine administered

For overall/dose:

N = number of administered doses

n/% = number/percentage of doses followed by at least one type of symptom whatever the study vaccine administered

95% CI = exact 95% confidence interval, LL = Lower Limit, UL = Upper Limit

Dose 2, 4 and 6 are the doses where subjects has received study vaccine - DTPa-IPV/Hib vaccine in Combo group and DTPa-IPV and Hib in Control group

CONFIDENTIAL
 116194 [DTPa-IPV (INFANRIX-IPV)-061]
 Statistical Analysis Plan Amendment 2 Final

**Template 13 Incidence of solicited local symptoms reported during the 4-day
(Days 0-3) period after vaccination following each dose and overall
(Total vaccinated cohort)**

Symptom	Type	Combo group					Control group				
					95 % CI					95 % CI	
		N	n	%	LL	UL	N	n	%	LL	UL
Dose 2											
Pain	All	224	108	48.2	41.5	55.0	227	113	49.8	43.1	56.5
	Grade 3	224	5	2.2	0.7	5.1	227	8	3.5	1.5	6.8
Redness (mm)	All	224	133	59.4	52.6	65.9	227	119	52.4	45.7	59.1
	>20	224	4	1.8	0.5	4.5	227	3	1.3	0.3	3.8
Swelling (mm)	All	224	65	29.0	23.2	35.4	227	64	28.2	22.4	34.5
	>20	224	5	2.2	0.7	5.1	227	2	0.9	0.1	3.1
Dose 4											

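### The exact intervals for primary-epoch per-dose reactogenicity rates treat three doses in one infant as independent, so they can be too narrow for common reactions that recur in the same infant

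*Protocol*

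**What the plan says.** Protocol 10.8 plans percentages of both subjects and doses with symptoms in Days 0-3, and the 4-day "solicited follow-up period will be tabulated with exact 95% CI [Clopper, 1934] after each vaccine dose and overall primary doses". SAP 6.4.1 repeats this: "solicited follow-up period will be tabulated with exact 95% CI after each vaccine dose and overall primary doses". SAP 11.1 names one method only: "The exact two-sided 95% CIs for a proportion within a group will be the Clopper-Pearson exact CI".

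The per-dose unit is set in SAP 11.2.2: "The incidence per dose is the number of vaccination visits at which an event was reported among all vaccination visits". SAP 11.2.5 then gives denominators by type of event. For solicited general symptoms the per-dose N is "All doses with solicited symptoms documented as present or absent within 0-3 days post dose"; for unsolicited symptoms it is "All study visits with study vaccine administered".

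The mock tables in SAP Annex 3 have an overall/dose block. In Template 12 (solicited and unsolicited combined) its footnote reads "N = number of administered doses"; in Template 13 (solicited local) N is the number of documented doses. Annex 3 says of its layouts: "These templates were copied from recent studies". They therefore show the intended format, not data from this trial.

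Neither document mentions within-infant correlation, a clustered variance, or a caveat on the per-dose interval.

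**The concern.** A Clopper-Pearson interval is exact for independent Bernoulli trials. The primary epoch gives each infant up to three doses, and those doses share the infant's own reactivity and usually the same parent filling in the diary card. If an infant who reacts to one dose is more likely to react to the next, 705 doses carry less information than 705 independent trials, and the interval does not respond to this.

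The choice of denominator (documented doses, administered doses or vaccination visits) does not alter the point, because each of them counts the same infant up to three times.

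At stake is the stated precision of the pooled per-dose reactogenicity rates. In a descriptive single-arm table, stating precision is the interval's only purpose.

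**Working it through.** 1. **Inputs.** About 235 infants (Protocol 10.3) and three primary doses each (Protocol 10.8), so up to 705 doses. The nominal level is 95%. Rho is not in the documents and is assumed over 0 to 0.4.

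2. **Reproducing the interval in the SAP layout.** The Clopper-Pearson limits for x events in n trials are the 2.5% quantile of Beta(x, n − x + 1) and the 97.5% quantile of Beta(x + 1, n − x). With n taken as the number of doses:
   - Template 13, pain, Combo: 276/672 gives 37.3 to 44.9, as printed.
   - Template 13, redness, Control: 365/681 gives 49.8 to 57.4, as printed.
   - Template 12, grade 3 any symptom, Combo: 72/672 gives 8.5 to 13.3, as printed.

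   The layout does apply a plain binomial interval to pooled doses (672 doses from 224 infants).

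3. **Effect on the variance.** With m = 3 doses per infant the variance is multiplied by 1 + (m − 1)rho = 1 + 2·rho, that is 1.2, 1.5 and 1.8 at rho 0.1, 0.25 and 0.4. The square roots are 1.10, 1.22 and 1.34.

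4. **Coverage of Clopper-Pearson.** Beta-binomial simulation, 235 infants × 3 doses, 20,000 trials per cell. The Monte Carlo standard error is √(0.95 × 0.05/20,000), about 0.15 points near 95%, and about 0.24 points near 86%. Coverage in %:

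| True rate per dose | rho 0 | 0.05 | 0.1 | 0.25 | 0.4 |
|---|---|---|---|---|---|
| 0.5% | 98.9 | 98.5 | 98.2 | 97.0 | 95.8 |
| 1% | 98.1 | 97.4 | 96.8 | 94.8 | 91.7 |
| 2% | 97.1 | 96.2 | 95.3 | 92.3 | 89.4 |
| 5% | 96.5 | 95.4 | 94.1 | 91.0 | 87.8 |
| 10% | 95.6 | 94.4 | 93.2 | 90.0 | 86.5 |
| 41% | 95.4 | 94.2 | 92.9 | 89.5 | 86.2 |

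   A larger run (200,000 trials per cell, 40% rate) gives 95.4, 94.2, 93.2, 90.9, 88.6 and 84.5 at rho 0, 0.05, 0.1, 0.2, 0.3 and 0.5, which is consistent.

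5. **Half-widths at 41%.** Clopper-Pearson: 3.69 points. Subject-clustered logit interval: 3.97, 4.43 and 4.85 points at rho 0.1, 0.25 and 0.4. The ratios are 3.97/3.69 = 1.08, 4.43/3.69 = 1.20 and 4.85/3.69 = 1.31.

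6. **Is clustering plausible?** Template 13 comes from another study and serves only as an illustration.
   - *Combo pain.* Independent doses would give 1 − (1 − 108/224)(1 − 81/224)(1 − 87/224) = 79.8% of infants affected; the table shows 143/224 = 63.8%. To bound rho, let a1, a2 and a3 be the infants with one, two and three painful doses. Then a1 + a2 + a3 = 143 and a1 + 2·a2 + 3·a3 = 276, so a2 + 2·a3 = 133. The concordant pairs, a2 + 3·a3, run from 133 (a3 = 0) to 199 (a3 = 66), out of 672 pairs. With p = 276/672 = 0.411, rho = (pairs/672 − p²)/(p(1 − p)), which runs from 0.12 to 0.53. Both extremes are compatible with the single-dose counts.
   - *Combo grade 3 pain.* Nine doses in nine infants: no concordant pairs, design effect 0.97, no clustering.

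7. **Does a clustered rule repair it?** The rule tested was Clopper-Pearson when fewer than five infants are affected and a subject-clustered logit interval otherwise. On the same trials its coverage, over the assumed rho values, is 94.4 to 95.2% at rates of 3% and above, 93.0 to 95.9% at 2%, 93.5 to 96.7% at 1% and 96.4 to 97.4% at 0.5%. An infant-level percentile bootstrap also works at 41% (94.6, 94.5 and 94.2% at rho 0.1, 0.25 and 0.4), but it covers only 83.1% at a 0.5% rate with rho 0.1.

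**The case against.** The strongest reply is that little depends on these rows. Safety is secondary, single-arm and descriptive, with no comparator, threshold or test. The same sentences plan overall per-subject and single-dose percentages, in which each infant counts once. At a 41% rate the half-width moves only from 3.7 to between 4.0 and 4.9 points. Rho is unknown here, and the only hint comes from another study's mock table, at 2, 4 and 6 months, which allows anything from slight to substantial clustering. All of this stands and sets the severity. It does not make the interval right: the per-subject rows estimate a different quantity (any reaction in an infant, not reactions per dose), so they do not correct the per-dose interval.

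A second reply concerns scope. For unsolicited events over Days 0-30, the text of Protocol 10.8 and SAP 6.4.1 plans intervals on subjects; a per-dose interval for unsolicited events alone appears only in mock Template 18. That is fair. The point rests on the pooled Days 0-3 rows, and it reaches Template 18 only if that layout is used.

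A third reply concerns the remedy. The cut-off of five infants has no source in the documents and makes the method depend on the data. The rule still undercovers somewhat at rates of 1 to 2% with strong clustering, and for the rarest events with weak clustering plain Clopper-Pearson is already adequate. This is also true, and it is why dropping the interval is offered as an equal option.

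**Conclusion.** The concern holds, as a minor point. As written, the method ignores up to three doses per infant, and the overall/dose interval is too narrow when a reaction is not rare and recurs in the same infants. For rates of 10% and 41%, a nominal 95% interval covers about 93% at rho 0.1, 90% at 0.25 and 86 to 87% at 0.4. At a 5% rate, coverage stays at or above 95% up to rho 0.05. At 1% or less there is little or no loss at small rho.

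These figures assume 235 infants, all three doses documented, a common rate at each dose and beta-binomial clustering. The conditional statement is firm; the size in this trial depends on a rho that the documents do not give. No study conclusion or immunogenicity result is affected.

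**What to change.** Add one sentence to SAP 6.4.1 or 11.1, for example: *For overall/dose rows of the primary epoch, the 95% CI will use a variance clustered on subject (logit-scale robust interval); if fewer than five infants have the event, the Clopper-Pearson interval will be shown with a footnote that it ignores within-infant correlation.* The same sentence should cover any per-dose unsolicited table that follows Template 18. Keep Clopper-Pearson for single-dose, overall/subject and booster rows.

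Alternatively, omit the interval from overall/dose rows and rely on the planned per-subject interval. A footnote alone would disclose the problem without correcting it.

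The cost is the sentence and a standard procedure call. At a 41% rate the intervals widen by about 8%, 20% and 31% at rho 0.1, 0.25 and 0.4. Two interval methods then appear in one table and need a footnote. Omitting the interval avoids that but gives up the precision statement for per-dose rates.

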10.9. Interpretation of analyses

All analyses will be conducted in a descriptive manner.

10.10. Conduct of analyses

Any deviation(s) or change(s) from the original statistical plan outlined in this protocol will be described and justified in the final study report.

10.10.1. Sequence of analyses

The analyses will be performed stepwise:

- A final analysis of the primary epoch will be conducted on all immunogenicity and safety data obtained up to one month after administration of the third primary dose of study vaccine (Visit 4), as soon as the data will be as clean as possible. This will include the analysis of the primary immunogenicity objectives related to the primary epoch and analysis of solicited symptoms and unsolicited symptoms reported within the 4-day (Days 0-3) period and 31-day (Days 0-30) period following the primary vaccination, respectively, and the SAEs reported during the primary epoch.
- Analysis of the booster epoch will be conducted on all cleaned immunogenicity and safety data obtained up to one month after administration of the booster dose of study vaccine (Visit 6). This will include analysis of the secondary immunogenicity objectives related to the booster epoch and analysis of solicited symptoms and unsolicited symptoms reported within the 4-day (Days 0-3) period and 31-day (Days 0-30) period following administration of the booster dose of study vaccine, respectively, and the SAEs reported during the booster epoch. At this second stage, in order to avoid missing SAEs that have been reported, an SAE summary table including all the events reported during the entire study period will also be generated.

10.10.2. Statistical considerations for interim analyses

All analysed data will be reported in an integrated clinical study report that will be written at the end of the study.

11. ADMINISTRATIVE MATTERS

To comply with ICH GCP administrative obligations relating to data collection, monitoring, archiving data, audits, confidentiality and publications must be fulfilled.

11.1. electronic Case Report Form instructions

A validated GSK defined electronic data collection tool will be used as the method for data collection.

In all cases, subject initials will not be collected nor transmitted to GSK. Subject data necessary for analysis and reporting will be entered/transmitted into a validated database or data system. Clinical data management will be performed in accordance with applicable GSK standards and data cleaning procedures.

While completed eCRFs are reviewed by a GSK Biologicals' Site Monitor at the study site, omissions or inconsistencies detected by subsequent eCRF review may necessitate clarification or correction of omissions or inconsistencies with documentation and approval by the investigator or appropriately qualified designee. In all cases, the investigator remains accountable for the study data.

The investigator will be provided with a CD-ROM of the final version of the data generated at the investigational site once the database is archived and the study report is complete and approved by all parties.

